1.3 Correlative Objectives

- 1.3.1 Measure baseline ⁶⁸gallium-dotatate (or Copper 64 dotatate) biodistribution.
- 1.3.2 Evaluate oral triapine plasma pharmacokinetics and corresponding methemoglobin level by venous blood gas proportion.
- 1.3.3 Collect blood at baseline and at disease progression to correlate result with clinical outcome. [NOTE: originally this blood was collected to analyze hPG80 but will now the frozen blood samples will be biobanked for future correlative analysis]
- 1.3.4 Describe the tumor molecular profile using whole exome sequencing (WES), as well as RNAseq by the National Clinical Laboratory Network (NCLN), and correlate it with treatment outcome.
- 1.3.5 Collect plasma for circulating DNA (ctDNA) assessment.
- 1.3.6 Assess the effect of triapine on single deoxyribonucleoside concentrations by an LC/MSMS assay in baseline (pre-treatment) and disease progression blood samples (processed to plasma).

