6.6 Duration of Follow-Up

Patients will be followed for 24 months from the time of enrollment *or* until death, whichever occurs first. Patients removed from study for unacceptable adverse event(s) will be followed until resolution or stabilization of the adverse event.

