9.5 Analysis of Secondary and Correlative Endpoints

ORR will be estimated along with 95% exact binomial confidence interval. PFS and OS will be estimated using the Kaplan-Meier curve and median estimates and confidence intervals will be calculated. Correlative endpoints such as radiographic expression of somatostatin receptors and changes from pre to post-treatment will be summarized using descriptive statistics and changes from baseline *vs.* follow-up time points will be assessed using paired test methodologies. WES data will be processed using the data processing and data analysis pipelines from the Biostatistics and Bioinformatics shared resource of MCC to identify candidate mutated genes with adjustment for false discovery rate. PK analysis will be performed and PK parameters will be estimated from patients enrolled in the dose escalation portion of the phase 1 trial. PK parameters will be compared with historical controls, and exploratorily, we may correlate exposure to toxicity, and incorporate data into a population PK model. Krenning score from the Gallium-68 Dotatate (or Copper-64 Dotatate) will be summarized by calculating the proportion of patients in each Krenning score category and exploratory assessments for association with clinical response (ORR) will be performed using Fisher's exact test. Median, interquartile range will be calculated for quantitative image measurements from Gallium-68 Dotatate (or Copper-64 Dotatate) and exploratory comparison of levels with clinical response (ORR) will be performed using two sample t-test or nonparametric analogs. Mean change in deoxynucleosides between baseline and post treatment samples will be assessed by paired t-test or other methods. Deoxynucleoside plasma concentration as a predictor of clinical outcomes will be explored by linear (progression free survival) and logistic regression (response).

Correlative endpoint analyses will be based on patients who received the RP2D from the dose escalation portion and expansion cohort. See details in Sections 6.3 and 9.4 for RP2D.

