blood collection (EDTA) for 1.3.3 – frozen blood will be biobanked for future analysis in lieu of hPG80 assay			X																								X	
ctDNA blood collection (Streck)			X																								X ^k	
Deoxyribonucleosides blood collection (EDTA) ^l			X								X																X	
Tumor tissue collection ^m		X																										
PK blood collection ⁿ				X																								

NCI Protocol #: 10388
 Version Date: 17.May.2023

	Screening	Pre-treatment ^a	Cycle 1 (8 weeks)							Cycle 2 (8 weeks)					Cycle 3 (8 weeks)					Cycle 4 (8 weeks)					Disease Progression	Follow-Up and Off-Treatment Visits ^{b,c}
			Day 1 ^c	Day 9	Day 14 ^c	Day 15 ^c	Day 29 ^c	Day 43 ^c	Days 44-56	Day 1 ^c	Day 14 ^c	Day 29 ^c	Days 30-56	Day 1 ^c	Day 14 ^c	Day 29 ^c	Days 30-56	Day 1 ^c	Day 14 ^c	Day 29 ^c	Days 30-56					
Methemoglobin Level by peripheral venous blood ^o			X	X																						

STUDY CALENDAR NOTES:

A: Triapine: Dose as assigned on Days 1-14 of each cycle. Cycle length = 8 weeks
The recommended Phase 2 Dose of Triapine was determined to be: 150mg once a day on Days 1-14 of each cycle. Cycle length = 8 weeks

B: Lutetium Lu 177 Dotatate: 200 mCi IV, Day 1 of each cycle for a total of 4 doses. Cycle length = 8 weeks.

a: Pre-treatment collections should be preferably collected on a separate day from screening, but may be collected on the same day at the discretion of the site.

b: Follow-up checks and surveillance CT/MRI scans to be conducted every 3-months for 24 months from the time of enrollment *or* until death, whichever occurs first. Patients removed from study for unacceptable adverse event(s) will be followed until resolution or stabilization of the adverse event. Additional scan not needed at the end-of-study visit.

c: Cycles 1-4 visit windows: Days 9,14 +/- 2 days. All other visits +/- 3 days.
Visit windows for Follow-up (Q3-mos visits): \pm 3 weeks visit windows.
The following exception applies to visit windows: Dosing of Lu-177 dotatate cannot be given prior to scheduled date. It can be delayed per visit windows in appropriate situations.

d: Performance status evaluations should be evaluated every 4 weeks.

e: Albumin, alkaline phosphatase, total bilirubin, bicarbonate, BUN, calcium, chloride, creatinine, glucose, LDH, phosphorus, potassium, total protein, SGOT [AST], SGPT [ALT], sodium.

f: To be performed if NETSPOT, DETECTNET (64Cu dotatate scan) or Octreoscan has not been performed within 6 months.

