g: 7 days +/- window is allowed for scans to accommodate logistical issues in obtaining timely scans for unforeseeable circumstances.

h: To confirm progression within the last 3 years.

i: Pregnancy test for women of childbearing potential.

j: 24-Hour Urine 5HIAA should be collected prior to dosing Lutetium Lu-177 dotatate. 24 Hr Urine 5HIAA should be collected unless in exceptional circumstances that patient cannot collect or deliver a 24-Hr sample, alternative 5HIAA assessment per institutional standard can be allowed.
5HIAA will also be collected at the end of PRRT treatment (clinic visit for Cycle 4 Day 29) or at disease progression, whichever happens first. If patient does not receive all 4 doses of PRRT then 24 Hr Urine 5HIAA can be collected at the end-of-treatment visit for that particular patient.

k: Optional collection.

l: Two 8mL K2 EDTA white top tubes will be collected at three timepoints for all participants on C1D1 (pre-treatment), on C2D1 (pre-treatment), and at disease progression.

m: If archival tissue within the last 6 months is not available, a fresh biopsy will be mandatory.

Screening	Pre-treatment ^a	Cycle 1 (8 weeks)							Cycle 2 (8 weeks)							Cycle 3 (8 weeks)							Cycle 4 (8 weeks)							Disease Progression	Follow-Up and Off-Treatment Visits ^{b,c}
		Day 1 ^c	Day 9	Day 14 ^c	Day 15 ^c	Day 29 ^c	Day 43 ^c	Days 44-56	Day 1 ^c	Day 14 ^c	Day 29 ^c	Days 30-56	Day 1 ^c	Day 14 ^c	Day 29 ^c	Days 30-56	Day 1 ^c	Day 14 ^c	Day 29 ^c	Days 30-56	Day 1 ^c	Day 14 ^c	Day 29 ^c	Days 30-56							

n: PKs: To be collected in the dose-escalation cohort only.

PK time points on Cycle 1, Day 9 (+/- 1 day) include: Pre, 0.5, 1, 1.5, 2, 3, 4, 6, 8 hours.

PK WINDOWS:

Pre dose: within 30 minutes

30 minutes: +/- 5 minutes

60 minutes: +/- 5 minutes

1 hour 30 minutes: +/- 5 minutes

2 hours: +/- 5 minutes

3 hours: +/- 10 minutes

4 hours: +/- 10 minutes

6 hours: +/- 10 minutes

8 hours: +/- 10 minutes

o: Methemoglobin: to be collected in dose-escalation cohort only, on Cycle 1 Day 1 and Cycle 1 Day 9.

Methemoglobin timepoint on Cycle 1 Day 1 is pre-treatment.

Methemoglobin timepoints on Cycle 1 Day 9 (+/- 1 day) include: Pre, 0.5, 1, 1.5, 2, 3, 4, 6, 8 hours, i.e., blood is to be drawn at each of the PK blood draws.

Methemoglobin Windows for C1D9 are:

Pre dose: within 30 minutes

30 minutes: +/- 5 minutes

60 minutes: +/- 5 minutes

1 hour 30 minutes: +/- 5 minutes

2 hours: +/- 5 minutes

3 hours: +/- 10 minutes

4 hours: +/- 10 minutes

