12.1.6 Progression-Free Survival

PFS is defined as the duration of time from registration to time of progressive disease as defined by RECIST 1.1 criteria or death from any cause, whichever occurs first.

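### Section 9.5 relates deoxynucleoside concentration to PFS by linear regression without saying how censored times enter or which blood sample is the predictor (minor, one exploratory analysis)

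*Combined protocol and SAP*

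**What the plan says.** Section 9.5 gives the deoxynucleoside assay two analyses. The first compares levels over time: "Mean change in deoxynucleosides between baseline and post treatment samples will be assessed by paired t-test or other methods". The second relates the level to outcome, which is to be "explored by linear (progression free survival) and logistic regression (response"). The latitude to use other methods belongs to the first sentence, not the second. For PFS itself the same section says "PFS and OS will be estimated using the Kaplan-Meier curve", a method that allows for censoring.

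Section 12.1.6 states: "PFS is defined as the duration of time from registration to time of progressive disease", with death as the alternative event. Section 6.6 states: "Patients will be followed for 24 months from the time of enrollment", or until death if that is earlier. Study Calendar note b agrees: "Follow-up checks and surveillance CT/MRI scans to be conducted every 3-months for 24 months from the time of enrollment". No section writes a censoring rule for PFS.

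On the samples, Study Calendar note l has tubes "collected at three timepoints for all participants on C1D1 (pre-treatment), on C2D1 (pre-treatment), and at disease progression". Objective 1.3.6 names fewer draws: concentrations are to be assessed "in baseline (pre-treatment) and disease progression blood samples (processed to plasma"). Section 9.5 does not say which draw, or which change between draws, is the predictor. Section 9.5 restricts correlative analyses to patients treated at the RP2D, and Section 9.1 takes 17 as the minimum number of these. Section 5.8 lists the assay as exploratory and fifth in priority among the blood assays.

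**The concern.** A patient who is alive and progression-free at 24 months has a PFS time known only to exceed 24 months. Ordinary linear regression has no place for that information. The analyst must either enter 24 months as if it were the event time or leave the patient out. Section 9.5 does not choose, and the two choices give very different analyses.

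The unnamed predictor is a separate gap. The progression sample exists only in patients who have progressed, and the date it is drawn is the outcome itself, so it cannot predict PFS. Objective 1.3.6 nevertheless lists it as one of two samples. The C2D1 value is known only about 8 weeks into treatment, so using it requires the clock to start there.

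At stake is whether the reported association can be interpreted and repeated. No trial decision hangs on it.

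**Working it through.** The plan attaches no power, event count or effect size to this analysis, so there is no stated figure to reproduce.

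**Inputs.** From the documents: n=17 (Section 9.1) and follow-up of 24 months (Section 6.6). Assumed, because the documents give no value: exponential PFS with median 12, 20, 30 or 40 months; a standardized predictor; hazard ratio 2 per SD; two-sided 5% tests. Each scenario uses 10,000 simulated trials unless stated.

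**1. How many are censored.** With no association, the share event-free at 24 months is 0.5^(24/median). For medians of 12, 20, 30 and 40 months this is 25%, 44%, 57% and 66%. Expected events among 17 are 17 × (1 − share) = 12.8, 9.6, 7.2 and 5.8.

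**2. What linear regression estimates.** If everyone is followed to 24 months, regressing min(PFS, 24) on concentration estimates the change in restricted mean PFS, which is a valid target. Its size depends on the cut-off. With median 30 months and follow-up of 18, 24, 36 and 48 months, the slope is −2.0, −3.2, −5.7 and −8.3 months per SD. The median Cox log hazard ratio is 0.74, 0.73, 0.73 and 0.73 (true value 0.69). That stability is partly built in, because the data were generated under proportional hazards.

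**3. Power at n=17, no early loss.**

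| Median PFS (months) | 12 | 20 | 30 | 40 |
|---|---|---|---|---|
| Censored at 24 months | 27.9% | 43.0% | 54.9% | 63.1% |
| Linear, all times | 51.6% | 42.6% | 34.8% | 29.7% |
| Cox, Wald | 54.9% | 46.1% | 36.0% | 29.6% |
| Wald minus linear (points) | 3.3 | 3.5 | 1.2 | −0.1 |
| Linear, censored dropped | 13.6% | 7.8% | 5.9% | 5.2% |

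The uncalibrated likelihood-ratio test shows 58.4%, 50.6%, 42.1% and 37.0%, but it rejects 5.5-6.4% of null trials, against 4.8-5.4% for linear. With both tests calibrated to 5% (40,000 trials), the likelihood ratio gives 54.8%, 46.1%, 39.9% and 33.3%, and linear gives 52.4%, 42.9%, 35.0% and 30.2%. The gain is 2.4, 3.2, 4.9 and 3.1 points.

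**4. Type I error.** With no early loss, linear regression holds its level. With 20% lost by 24 months for reasons unrelated to concentration, it rejects 4.6-5.1% of null trials. If 20% are lost at average concentration and the loss hazard doubles per SD, linear rejects 6.4%, 7.5%, 9.0% and 10.0% across the four medians. The Cox score test stays at about 5-6%.

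**5. Precision of a Cox fit.** The rough factor exp(1.96/√events) gives 1.75 at 12.3 events and 2.18 at 6.3 events (the mean counts at hazard ratio 2). It is too optimistic here. The median factor from fitted models is 2.06, 2.20, 2.42 and 2.63, so the 95% CI spans roughly 2.1 to 2.6 times either side of the hazard ratio.

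**6. The predictor.** By step 1, at most about 6 to 13 of 17 patients could supply a progression sample, and only once the outcome has occurred. For C2D1 at 56 days (1.84 months), the share with an earlier event is 1 − 0.5^(1.84/median), or 10.1%, 6.2%, 4.2% and 3.1%. A landmark start loses few patients.

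**The case against.** The strongest reply is that linear regression is usable here. Follow-up is a fixed 24 months from enrollment for every patient, and Section 2.5.2.1 notes that accrual has closed, so late entry need not shorten anyone's follow-up. Under that condition, the restricted-mean reading in step 2 is sound. This stands. A reader might infer that linear regression cannot represent patients censored at 24 months and is therefore invalid. The documents do not support that. Censoring at one common time is the case that truncated-time regression can handle. What remains is that Section 9.5 does not name this target, does not rule out dropping censored patients, and offers no protection against earlier loss. The support for earlier loss is limited: Section 6.5 lists withdrawal from the study among reasons for ending treatment, and no loss rate is given.

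A reader might also expect Cox regression to be clearly more powerful. It is not. By the Wald interval that usually accompanies a hazard ratio, the gain at n=17 is close to nil for long median PFS, and the simulations favor Cox by assuming proportional hazards.

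Finally, it can be said that the word predictor already excludes a sample drawn at the event. That is the sensible reading. But objective 1.3.6 names that sample and omits C2D1, so the choice should not be left to inference.

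**Conclusion.** The point holds as a minor one. Section 9.5 names a method for a time-to-event outcome without saying how censored times enter it, and leaves the predictor open among samples of which one cannot serve.

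The practical size depends on what the analyst does. Entering all times under complete follow-up costs little power and keeps type I error near 5%, but yields a slope tied to the 24-month limit. Dropping censored patients removes nearly all power. Loss related to concentration can raise false positives modestly. A reader might infer from that last result that false positives are to be expected in this trial. Nothing in the documents suggests that loss depends on concentration, and the 6-10% rests wholly on the assumed 20% loss and doubling hazard.

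All percentages rest on assumed exponential PFS, medians and effect size. The scope is one exploratory analysis. The hypothesis in Section 2.5.4, a rise in level after triapine, is tested separately by the paired comparison. The RP2D, ORR and Kaplan-Meier estimates of PFS and OS are not affected.

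**What to change.** Replace the PFS part of the sentence in Section 9.5 with:

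> The association of deoxynucleoside plasma concentration with PFS will be explored by Cox proportional hazards regression (or another censored-data model). Patients without progression or death are censored at their last evaluable tumor assessment, and the same rule applies to the Kaplan-Meier PFS analysis. The hazard ratio is reported with its 95% CI as exploratory. The predictor is the C1D1 pre-treatment concentration; a second analysis uses the C1D1-to-C2D1 change, with time counted from C2D1 in patients event-free at C2D1. The disease-progression sample is not used as a predictor.

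The censoring rule has to be written out because no section now contains one. The second analysis is included because the C1D1 sample precedes triapine, while the stated hypothesis concerns the level afterwards. Objective 1.3.6 should also list the C2D1 draw, to match the Study Calendar.

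The cost is wording and slightly more analysis work, with the same samples and data. The result becomes a hazard ratio instead of a slope in months, and with about 6 to 12 events it will still be imprecise (step 5).

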The efficacy of Lutetium Lu 177 Dotatate in patients with foregut, midgut, and hindgut GEP-NETs was assessed in 360 patients in the ERASMUS study (Package Insert, 2018). In ERASMUS, Lutetium Lu 177 Dotatate was initially provided as expanded access under a general peptide receptor radionuclide therapy protocol at a single site in the Netherlands. A subsequent Lutetium Lu 177 Dotatate-specific protocol written eight years after study initiation did not describe a specific sample size or hypothesis testing plan but allowed for retrospective data collection. A total of 1214 patients received Lutetium Lu 177 Dotatate in ERASMUS, of which 601 (50%) were assessed per RECIST criteria. Of the 601 patients evaluated by investigators using RECIST criteria, 360 (60%) had GEP-NETs. Lutetium Lu 177 Dotatate 200 mCi was administered every 6 to 13 weeks for up to 4 doses concurrently with the recommended amino acid solution. The major efficacy outcome was investigator-assessed ORR. The median age in the efficacy subset was 61 years (25 to 88 years), 52% were male, 61% had a baseline Karnofsky performance status \geq 90 (60 to 100), 60% had progressed within 12 months of treatment, and 15% had received prior chemotherapy. Fifty five percent of patients received a concomitant somatostatin analog. The median dose of Lutetium Lu 177 Dotatate was 800 mCi. Baseline tumor assessments were

obtained in 39% of patients. The investigator assessed ORR was 16% (95% CI 13, 20) in the 360 patients with GEP-NETs. Three complete responses (CRs) were observed (<1%). Median DOR in the 58 responding patients was 35 months (95% CI: 17, 38).

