6.3 Triapine Administration: Dose Expansion Cohort

This study's dose escalation cohort enrolled 15 patients in order to identify the recommended Phase 2 Dose (RP2D) of Triapine. The Recommended Phase II Dose (RP2D) is based on data available from 15 patients who were treated with varying doses of Triapine (100mg, 150mg and 200mg) using BOIN dose escalation design.

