9. STATISTICAL CONSIDERATIONS

9.1 Study Design/Endpoints

This study is a multicenter phase 1 trial of triapine and Lutetium Lu 177 Dotatace in combination for well-differentiated somatostatin receptor-positive GEP-NETs after the failure of at least one line of prior systemic cancer treatment. An expansion cohort with 14 additional patients will be enrolled at the RP2D to further assess safety, obtain initial estimates of clinical response outcomes, and perform exploratory comparisons of biomarkers.

The primary objective of the **phase 1 trial** is to determine the MTD and identify the RP2D of triapine in combination with Lutetium Lu 177 Dotatace. The Bayesian optimal interval design (BOIN) (Yuan *et al.*, 2016) will be employed to guide dose escalation. DLT is defined in Section 6.2 and will be assessed after the first cycle (8 weeks post treatment). Patients will be enrolled in cohorts of 3 beginning at dose level 1. A target DLT rate of 25% will be assumed with dose escalation, λ_e , and de-escalation boundaries, λ_d , set at 0.197 and 0.298, respectively. Based on the BOIN design, dose escalation will proceed as shown in the table below until a total of 15 patients have been enrolled in the dose escalation part of this phase 1 trial. MTD and RP2D will be estimated using isotonic regression based on toxicity data from all patients.

Dose escalation and de-escalation boundaries Table

Number of patients treated at the current dose:	1	2	3	4	5	6	7	8	9	10	11	12	13	14	15
Escalate if DLTs \leq	0	0	0	0	0	1	1	1	1	1	2	2	2	2	2
De-escalate if DLTs \geq	1	1	1	2	2	2	3	3	3	3	4	4	4	5	5

An expansion cohort with 14 additional patients will be enrolled at the RP2D to further assess safety, obtain initial estimates of clinical response outcomes, and perform exploratory comparisons of biomarkers. Assuming that the minimum number of patients enrolled at the RP2D is equal to 17, the proposed sample size from the phase 1 portion and expansion cohort will produce a two-sided 95% exact confidence interval with a width equal to 0.44, when the DLT rate is 0.25.

Interim Analysis for Phase 1 (Dose escalation)

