9.4.1 Results of the dose escalation phase (interim analysis of Phase 1)

The Phase 1 dose escalation enrolled 15 patients using the BOIN design. Isotonic regression provided posterior estimates of the DLT rate at each dose level. The DLT estimate for DL2 = 0.18, 95% credible interval: (0.03, 0.045) and at DL2 the Prob (DLT rate > 0.25) = 0.25. All evaluable patients completed the DLT window.

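### With about 3 to 7 responders expected, the logistic regression of response on deoxynucleoside level in Section 9.5 would be better pre-specified as Firth-penalised; this is a minor, cheap improvement with small costs

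*Combined protocol and SAP*

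**What the plan says.** Section 9.5 of the combined protocol and SAP states: "Deoxynucleoside plasma concentration as a predictor of clinical outcomes will be explored by linear (progression free survival) and logistic regression (response". It restricts the population: "Correlative endpoint analyses will be based on patients who received the RP2D from the dose escalation portion and expansion cohort". For the part given as "logistic regression (response", it does not say how the logistic model is fitted, what interval or test goes with it, or what happens if there are very few responders or if the marker separates responders from non-responders completely. The same section does provide for small numbers elsewhere: an exact binomial interval for the response rate, Fisher's exact test for the Krenning score, and nonparametric alternatives for the imaging measures.

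No number of responders is projected for this analysis. The size of the population has to be pieced together from Section 9.1 ("An expansion cohort with 14 additional patients will be enrolled at the RP2D" and "Assuming that the minimum number of patients enrolled at the RP2D is equal to 17"), Section 6.3 ("15 patients who were treated with varying doses of Triapine (100mg, 150mg and 200mg) using BOIN dose escalation design") and Section 9.4.1 ("The DLT estimate for DL2 = 0.18"). Section 5.8 labels the deoxyribonucleoside assay exploratory.

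**The concern.** Maximum-likelihood estimates of a log odds ratio are biased away from zero when the rarer outcome has only a handful of events. They are not finite when the predictor separates the two groups. With 3 to 7 responders both problems are live. At stake is the size of the association that is reported: an exploratory odds ratio that is too large on average, with a long upper tail, gives a poor picture of the marker. A second point is conduct. If separation occurs and no method has been named, the analyst must choose one after seeing the data.

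**Working it through.** **The plan's own figure.** The only sample-size figure covering these patients is the exact 95% interval width of 0.44 for the DLT rate in Section 9.1. Clopper-Pearson with n = 17 and x = 0.25 × 17 = 4.25 gives 0.076 to 0.514, width 0.438. The figure reproduces, but it says nothing about the regression.

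**How many patients.** The expansion cohort adds 14. Escalation put 15 patients on three dose levels in cohorts of 3, so level 2 holds 3 to 9, and the total is 14 + 3 = 17 to 14 + 9 = 23. Section 9.4.1 gives a level 2 estimate of 0.18 and a probability of 0.25 that the DLT rate exceeds 0.25. One DLT in 9 with a uniform prior gives Beta(2, 9): mean 2/11 = 0.182, and P(rate > 0.25) = 0.75^10 + 10 × 0.25 × 0.75^9 = 0.244. That fits 9 patients and a total of 23. This is an inference; no total is stated.

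**How many responders.** Section 2.3 reports "The investigator assessed ORR was 16% (95% CI 13, 20" for Lu-177 dotatate alone, and Section 2.4 cites 2% complete plus 28% partial responses, 30% in all.
- n = 17: 0.16 × 17 = 2.7 and 0.30 × 17 = 5.1.
- n = 23: 0.16 × 23 = 3.7 and 0.30 × 23 = 6.9.

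The response-evaluable rule in Section 12.1.1 (at least three cycles) can only lower these counts.

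**Simulation.** The model is logit P(response) = α + βx, with x scaled to SD 1. Maximum likelihood (ML) maximises l(α, β). Firth maximises l(α, β) + ½ log |I(α, β)|, where I is the information matrix. ML is summarised over data sets without separation and Firth over all data sets, which favours ML. The effect size, the shape of x and the response rate are assumptions. The table takes β = 0.7 (odds ratio about 2 per SD); inflation is (mean − 0.7)/0.7.

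| Setting | ML mean | ML median | Firth mean | Firth median | RMSE ML / Firth |
|---|---|---|---|---|---|
| n = 23, normal x, ORR 16% | 0.974 (+39%) | 0.771 (+10%) | 0.711 (+2%) | 0.623 (−11%) | 1.53 / 0.80 |
| n = 23, normal x, ORR 23% | 0.930 (+33%) | 0.770 (+10%) | 0.715 (+2%) | 0.638 (−9%) | 1.22 / 0.69 |
| n = 23, normal x, ORR 30% | 0.899 (+28%) | 0.767 (+10%) | 0.712 (+2%) | 0.642 (−8%) | 1.18 / 0.62 |
| n = 23, log-normal x, ORR 30%, 4–7 responders | 0.877 (+25%) | 0.774 (+11%) | 0.711 (+2%) | 0.637 (−9%) | 1.05 / 0.69 |
| n = 17, normal x, ORR 25%, 4–7 responders | 1.017 (+45%) | 0.803 (+15%) | 0.738 (+5%) | 0.638 (−9%) | 1.45 / 0.75 |

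**Range over other settings.**
- n = 23, 4–7 responders, β from 0.5 to 1.0: ML mean inflation +28% to +38% with a normal x, +18% to +35% with a log-normal x.
- n = 17, 4–7 responders: +36% to +51%. Firth with 4–7 responders: about 0% to +7%.
- No true association and a normal x: no bias. With a log-normal x, the ML mean is −0.13 to −0.17.
- Separation: 0% to 3.4% with 4–7 responders, about 5% at n = 17, ORR 16% and β = 0.7. In a further 0.84^17 = 5% or so of such trials nobody responds, and neither method can inform.

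The ML error depends on a few near-separated fits. At n = 23, ORR 23% to 30% and β = 0.7 it ranges over about 0.9 to 1.2, against 0.6 to 0.7 for Firth.

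**Costs of Firth.** Mean predicted response rises above the observed rate: 0.230 to 0.248 at n = 23, ORR 23%, and 0.169 to about 0.20 at n = 17, ORR 16%. Power at n = 23, ORR 23%, β = 0.7 is 0.224 for the penalised likelihood-ratio test against 0.285 for the ML one. Part of that gap arises because the ML test is mildly anti-conservative (size 0.065 to 0.07, against about 0.04). Firth Wald tests are far too conservative (size about 0.003 to 0.01), so profile intervals are needed.

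**The case against.** Four readings go further than the material allows, and the case against them stands.

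1. *A reader might infer that this trial's estimate will be a third too large.* The 25% to 40% is a mean, pulled up by a long right tail, and it needs a true association. The median ML estimate is only about 10% high, and the median Firth estimate misses by a similar amount in the other direction. Firth's fair advantage is its smaller mean bias together with its lower variance.
2. *A reader might infer that markers would be wrongly chosen.* This is not shown. At n = 23 the ML and Firth slopes have a rank correlation of 0.985 to 0.998, so markers would be ordered almost identically. Nor could either estimate size a later study: the Firth estimate itself has an SD of about 0.6 to 0.75.
3. *A reader might infer that Firth is free.* It is not, as the costs above show.
4. *A reader might infer that the plan specifies a wrong method.* Section 9.5 names no estimator, and Firth's method is itself a form of logistic regression. Maximum likelihood is the default reading, not the wording.

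The stakes are also low. The stated hypothesis in Section 2.5.4 concerns a rise in plasma deoxynucleosides, which Section 9.5 assesses by a paired comparison, and no decision rule depends on this regression. The trial also hopes to improve on the response rates of Lu-177 dotatate alone, so the responder count could exceed 7.

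What survives is narrow: at the numbers that the documents suggest, the default fit has more mean bias and more error than a standard alternative, and it can fail outright.

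**Conclusion.** The point holds as a minor improvement. With 17 to about 23 patients and about 3 to 7 responders, the default maximum-likelihood fit overstates the mean log odds ratio by roughly 20% to 50% when an association exists, and by about 25% to 40% near n = 23. Firth's method removes nearly all of that mean bias and cuts the root mean squared error by about a third or more.

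This rests on assumptions that the documents do not settle: response rates borrowed from Lu-177 dotatate alone, an inferred upper count of 23, a single normal or log-normal predictor, and a moderate true effect. It does not rescue the analysis. Penalised likelihood-ratio power for an odds ratio of about 2 per SD stays at only about 18% to 26% at n = 23 for response rates of 16% to 30% (normal predictor), so the result remains exploratory under either method.

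**What to change.** In Section 9.5, replace the words on logistic regression for response with: *Firth penalised logistic regression (response), one predictor per model, with profile penalised-likelihood confidence intervals, and an intercept correction (e.g. FLIC) if predicted probabilities are reported.*

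This costs one phrase and uses standard software. The statistical price is a median log odds ratio about 5% to 15% too small, a mean predicted response 1 to 3 percentage points too high if the intercept correction is left out, and slightly lower power than the mildly anti-conservative maximum-likelihood likelihood-ratio test. Reporting the number of responders beside the estimate would let readers judge how little information it carries.
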